## 1. INTRODUCTION AND BACKGROUND

Acne vulgaris is a disorder of the pilosebaceous unit. Found in greatest concentrations on the face, upper back, shoulders and chest, a pilosebaceous unit is made up of a hair follicle lined with keratinocytes, a sebaceous gland, and a hair. The sebaceous gland produces a substance called sebum. Although sebum normally empties onto the skin's surface through the openings of the follicles, the follicles may become plugged with hair, sebum and keratinocytes, resulting in comedones. Bacteria normally found on the skin may grow in the comedones, resulting in inflammation. Therefore, acne vulgaris is a multi-factorial disease, caused by the interplay of excess sebaceous gland secretion, bacterial growth, keratinization abnormalities, and immune reactivity.

Acne is clinically characterized by the formation of open and closed comedones (non-inflammatory lesions), papules, pustules and nodulocystic lesions (inflammatory lesions). The highest concentration of lesions is often found on the face, shoulders, upper back, and chest. Although acne vulgaris is most common in adolescents and young adults, it can continue to occur in adults older than 50 years of age.

Taro has developed a new formulation [*Redacted as ATS55*], for treatment of acne in patients 9 years of age and older. [*Redacted*] The current study is designed to evaluate the safety and efficacy of this new formulation. Efficacy results will be used to calculate the sample size and establish endpoints for the Phase 3 studies.

## 2. OBJECTIVES

The objective of this study to evaluate the efficacy and safety of [*Redacted as ATS55*] (Taro Pharmaceuticals U.S.A, Inc.) in the treatment of acne vulgaris.

## 3. STUDY OVERVIEW

Subjects will be admitted into the study after informed consent/assent has been obtained, a medical history and physical examination (with vital signs) have been performed and inclusion/exclusion criteria have been met. Subjects must have a clinical diagnosis of acne vulgaris to qualify for inclusion in this study.

Approximately 300 Subjects will be assigned in a 1:1 ratio to treatment with the test product, [*Redacted as ATS55*] (Taro Pharmaceuticals U.S.A., Inc.) or placebo (vehicle of the test product) in this multiple-center, double-blind, randomized, placebo controlled, parallel-group study. The assigned Investigational Product will be self-applied topically to the face and other affected body areas once daily for 84 consecutive days. The Investigational Product should be applied around the same time every day after the Subject's treatment areas have been washed with a non-medicated cleanser, and warm water. For the purposes of this study, the face is considered to start at the hairline and end at the jaw line and excludes the eyes, the lips and all mucous membranes. The body is considered as at least one affected area: back, chest and/or shoulders. Subjects will be required to use diaries to document the date of study treatments, any missed treatments and the occurrence of all adverse events.

The duration of each Subject's participation in the study will be 84 days. Scheduled study visits will include:

Visit 1: Screening/Baseline Visit (Day 0); Visit 2: Interim Visit (Week 2 / Day 14 ± 4 Days); Visit 3: Interim Visit (Week 4 / Day 28 ± 4 Days); Visit 4: Interim Visit (Week 6 / Day 42 ± 4 Days); Visit 5: Interim Visit (Week 8 / Day 56 ± 4 Days); Visit 6: Interim Visit (Week 10 / Day 70 ± 4 Days); Visit 7: End of Treatment Visit (Week 12 / Day 84 ± 4 Days) Visit 8\*: Follow up phone call (Week 13 / Day 91 ± 4 Days) \*if required for on-going AEs based on PI decision

A nine (9) day window (i.e., ± 4 days) will be considered acceptable for each scheduled visit following

the baseline visit.

An Unscheduled Visit is allowed at any time, for any reason, if in the Principal Investigator's opinion it is warranted. If a Subject is discontinued from the study during an Unscheduled Visit, the Unscheduled Visit will be referred to as an Early Discontinuation Visit and all procedures scheduled for Visit 7 will be performed. If the Unscheduled Visit is not an Early Discontinuation Visit (i.e., the Subject will continue to take part in the study), then all procedures will be performed and treated as an interim visit, with the exception of the collection of Investigational Product and Subject diaries from Subjects.

If the Principal Investigator determines that the Subject's condition has worsened to the degree that it is unsafe for the Subject to continue in the study, the Subject may be discontinued from the study as a treatment failure and the Subject may be treated using the standard care.

At the screening/baseline visit, a physical examination (with vital signs) will be conducted. At each subsequent visit, the following procedures will be performed: counts of the facial comedones (open and closed), papules, pustules, nodules and cysts lesions will be performed, the Investigator's Global Evaluation (IGA) will be performed and the signs and symptoms of irritation will be assessed.

Safety will be assessed by the monitoring of all adverse events and the monitoring of any signs and symptoms of local irritation.

At Visit 1, an informed consent/assent and HIPAA authorization will be obtained from the potential study Subject before any study procedures take place. After the Subject has been consented/assented, the Subject's medical history will then be documented, including the Subject's concomitant medications. A urine pregnancy test will be performed for female Subjects of childbearing potential. All female Subjects are considered to be of childbearing potential unless they are premenarchal, have been surgically sterilized or have been postmenopausal for at least 1 year. A baseline acne grade will be assigned to the Subject using the Investigator's Global Assessment (IGA) and a baseline lesion count will be performed. The Subject will undergo a brief physical examination, including the recording of vital signs. The Subject will be evaluated for signs and symptoms of local irritation. The Subject will be reviewed against the inclusion/exclusion criteria. Blinded Investigational Product will be dispensed to Subjects who meet all of the inclusion and exclusion criteria using the lowest patient randomization number available at that investigative site. Subjects will be instructed on the application of Investigational Product and completion of Subject diaries. The Investigational Product should not be opened in the clinic. The first application of Investigational Product will be reviewed.

Subjects will return to the study site for visits at Weeks 2, 4, 6, 8, 10, and 12. The Subject's concomitant medications will be reviewed and documented. A urine pregnancy test will be performed for female Subjects of childbearing potential. The Subject will be evaluated for signs and symptoms of local irritation and any adverse events will be documented. The Subject's facial acne will be assessed using the IGA, the Subject's lesions will be counted and these results will be documented. The Subjects are instructed to bring their used Investigational Product and their study diaries to each study visit. Compliance with drug applications will be assessed at each visit. Additional units of Investigational Product will be dispensed and each Subject will receive new diaries during visits at Weeks 2, 4, 6, 8, and 10. In addition, all Investigational Product and diaries will be collected from the Subject during each scheduled visit or the Early Discontinuation Visit.

## **Study Visit Schedule**

|   | Visit 1   | Visit 2            | Visit 3            | Visit 4            | Visit 5            | Visit 6             | Visit 7                |
|---|---|--------------------|--------------------|--------------------|--------------------|---------------------|------------------------|
| PROCEDURE   | Screening /
Randomization
/ Baseline /
Treatment start | Interim - 1        | Interim - 2        | Interim - 3        | Interim - 4        | Interim - 5         | EOT/UV/ED  |
| Day   | 0   | 14 ± 4
(week 2) | 28 ± 4
(week 4) | 42 ± 4
(week 6) | 56 ± 4
(week 8) | 70 ± 4
(week 10) | 84 ± 4
(week 12)    |
| Informed Consent/Assent
and HIPAA  | Х   |                    |                    |                    |                    |                     |                        |
| Demographics  | Х   |                    |                    |                    |                    |                     |                        |
| Medical History   | Х   |                    |                    |                    |                    |                     |                        |
| Concomitant Medication  | Х   | Х                  | Х                  | Х                  | Х                  | Х                   | Х                      |
| Brief Physical Examination
including Vital Signs                                 | х   |                    |                    |                    |                    |                     |                        |
| Urine Pregnancy Test    | Х   | Х                  | Х                  | Х                  | Х                  | Х                   | Х                      |
| Inclusion/Exclusion Criteria  | Х   |                    |                    |                    |                    |                     |                        |
| Local Irritation Assessment   | Х   | Х                  | Х                  | Х                  | Х                  | Х                   | Х                      |
| Lesion Counts   | Х   | Х                  | Х                  | Х                  | Х                  | Х                   | Х                      |
| Investigator's Global
Assessment (IGA)   | х   | Х                  | х                  | х                  | х                  | х                   | Х                      |
| Randomization   | Х   |                    |                    |                    |                    |                     |                        |
| Adverse Event Reporting   | X   | Х                  | Х                  | Х                  | Х                  | Х                   | Х                      |
| Investigational Product
Dispensing / Diary
Dispensing                         | х   | х                  | х                  | х                  | х                  | х                   |                        |
| Investigational Product
Return / Diary Collection                                |   | х                  | х                  | х                  | х                  | х                   | X          |
| Diary Review  |   | Х                  | Х                  | Х                  | Х                  | Х                   | Х                      |
| Investigational Product
Accountability   |   | Х                  | Х                  | Х                  | Х                  | Х                   | х                      |
| Review of Instructions with
Subject (including Diary
Completion Instructions) | х   | х                  | х                  | х                  | х                  | х                   |                        |
| Treatment Area Photograph**   | Х   | Х                  | Х                  | Х                  | Х                  | Х                   | Х                      |
| Schedule next visit   | Х   | X                  | X                  | Х                  | X                  | Х                   |                        |

EOT - End of Treatment, UV - Unscheduled Visit, ED - Early Discontinuation Visit

 The urine pregnancy test is to be conducted for women of child-bearing potential. Tubal ligation is not considered equivalent to female sterilization. Women with a history of tubal ligation are still considered females of childbearing potential and must complete a urine pregnancy test.

Any AEs reported after signing Informed Consent should be reported.  Investigational product and Subject Diaries will be collected from patients during Visit 7 (End of Treatment Visit) or the Early Discontinuation Visit.

\*\* two sites will be designated to take pictures of the treatment areas from designated subjects from Subgroup at each Clinic Visit

## 4. STUDY POPULATION

## 4.1 Number of Subjects

This multi-center study will be comprised of Subjects presenting with a clinical diagnosis of acne vulgaris of severity grade 2, 3, or 4 using the IGA. Approximately 300 Subjects will be enrolled into the study. Male and female Subjects,  $\geq$  9 years of age, of any race, who meet the inclusion and exclusion criteria, will be enrolled in approximately 5 study sites. Approximately equal numbers of male and female subjects will be enrolled to each of the study arms.

## 4.2 Inclusion Criteria

[Redacted]

## 4.3 Exclusion Criteria

[Redacted]

## 4.4 Prohibited Medications, Procedures, and Activities

#### [Redacted]

## 4.5 Precautions

The following precautions are to be taken during this study:

- 1. To minimize exposure to sunlight, a wide-brimmed hat or other protective clothing should be worn. The non-comedogenic sunscreen with a SPF 15 rating or higher provided by the Sponsor may be used.
- 2. Exposure to weather extremes including strong wind or cold should be avoided.
- 3. The Investigational Product should not be applied to cuts, abrasions or eczematous skin.
- 4. The Investigational Product should not be applied to the eyes, the lips, the angles of the nose or any mucous membranes.

If a reaction suggesting sensitivity or chemical irritation occurs, the Principal Investigator should assess the Subject's condition as soon as possible (i.e., during an Unscheduled Visit) and determine whether treatment should be discontinued. If the Subject is discontinued from the study during an Unscheduled Visit, procedures from Visit 4 should be followed and the visit will be referred to as an Early Discontinuation Visit.

## 4.6 Subject Disposition and Discontinuation

Investigators are urged to enroll only those eligible Subjects who are likely to complete the entire study and who are willing to comply with the protocol-specified procedures. It is the right and duty of the investigator to interrupt the treatment of any Subject whose health or well-being may be threatened by continuation in this study, or who may be experiencing unmanageable factors that may interfere with the study procedures and/or the interpretation of study results. Such Subjects should be withdrawn from the study rather than continued under a modified regimen.

Subjects will be removed from the study for any of the following reasons:

- If the Subject withdraws his or her consent for any reason;
- If the Subject's condition has worsened beyond grade 4 or to the degree that the Principal Investigator feels it is unsafe for the Subject to continue in the study;

- If the Subject's drug code is unblinded;
- If an adverse event occurs for which the Subject desires to discontinue treatment or the Principal Investigator determines that it is in the Subject's best interest to be discontinued;
- If there is a significant protocol violation;
- If the Subject is lost to follow-up;
- If the Subject becomes pregnant;
- If the Subject becomes a prisoner or become involuntarily incarcerated;
- Any other reason that may affect the outcome of the study or the safety of Subjects; or
- Termination of the study by the Sponsor.

A significant protocol violation is defined as any Subject or Investigator activity that could have possibly interfered with the therapeutic administration of the treatment or the precise evaluation of treatment efficacy.

The reasons for a Subject discontinuation will be documented. If a Subject is discontinued from the study for any reason, the procedures scheduled for Visit 7 will be completed and any outstanding data and study drug should be collected if possible. Data, in addition to the reason for discontinuation and the date of removal, will be documented on the End of Study eCRF.

Before a Subject is considered to be lost to follow-up, the Principal Investigator will document all attempts to reach the Subject twice by telephone and will send a certified follow-up letter.

In the event that a Subject discontinues from the study at any time due to an adverse event, the reason for discontinuation, the nature of the event and its clinical course must be fully documented. For such a Subject, the Principal Investigator must strive to follow the Subject until the adverse event has resolved, become clinically insignificant, is stabilized or the Subject is lost to follow-up. Should a serious adverse event be noted, procedures stated in Section 10.3 must be followed.

## 5. SAFETY AND TOLERABILITY EVALUATIONS

## 5.1 General Safety Evaluations

A complete medical history will be obtained for the Subject's current and past medical conditions. Significant medical history should include, but not be limited to, evidence of hypertension, lipid disorders, obesity, heart attack, stroke, congestive heart failure, kidney disease, auto immune disease and gestational diabetes. Significant surgical history should include, but not be limited to, removal of blockage from an artery and gallbladder removal.

Concomitant medications, including the use of sunscreen, in addition to the reason for the medication use, will be assessed at baseline and at each subsequent study visit. The start and stop date of concomitant medication use during the study should be provided in the data set in addition to the reason for the medication use.

A brief physical examination will be performed at baseline. The physical examination will include, at a minimum, examination of the Subject's general appearance, skin, HEENT (head, eyes, ears, nose and throat), heart, lungs, musculoskeletal system, neurological system, lymph nodes, abdomen and extremities. The Subject's body weight will also be measured while the Subject is lightly clothed (e.g., no coat or shoes).

## 5.2 Physical Examination

The investigator, sub-investigator or appropriately delegated designee, (Physician's Assistant, Advanced Registered Nurse Practitioner, and Registered Nurse as per local regulations) will perform a brief physical examination, prior to the Subject starting study drug.

Vital signs, including blood pressure, pulse rate, respiratory rate and oral body temperature will be documented at Visit 1. Vital signs will be measured after the Subject has rested in a seated position for at least 5 minutes.

The Subject's body weight will also be measured while the Subject is lightly clothed (e.g., no coat or shoes). Height will be measured without shoes.

## 5.3 Pregnancy Test

All female Subjects of childbearing potential will undergo a urine pregnancy test during Visit 1 and at each subsequent study visit. All female Subjects are considered to be of childbearing potential unless they are premenarchal, have been surgically sterilized or have been postmenopausal for at least 1 year. Women of childbearing potential, in addition to having a negative urine pregnancy test, must be willing to use an acceptable form of birth control during the study from the day of the first dose administration to 30 days after the last administration of study drug For the purpose of this study the following are considered acceptable methods of birth control: oral or injectable contraceptives, contraceptive patches, Depo-Provera® (stabilized for at least 3 months), NuvaRing® (vaginal contraceptive), Implanon™ (contraceptive implant), double barrier methods (e.g. condom and spermicide), IUD, or abstinence with a 2nd acceptable method of birth control should the Subject become sexually active. A sterile sexual partner is NOT considered an adequate form of birth control.Subjects on hormonal contraception must be stabilized on the same type for at least three months prior to enrollment in the study and must not change the method during the study. Subjects who had used hormonal contraception and stopped must have stopped no less than three months prior to the study.

## 5.4 Concomitant medications

Concomitant medications, including the use of sunscreen, in addition to the reason for the medication use, will be assessed at baseline and at each subsequent study visit. The start and stop date of concomitant medication use during the study should be provided in the data set in addition to the reason for the medication use.

A record of concomitant medications taken by the Subject is to be obtained using generic name, if known, with the corresponding indication. The medications to be recorded will include prescription and over-the-counter (OTC) medications and dietary supplements. All medications taken on a regular basis, including aspirin and acetaminophen, should be recorded.

## 5.5 Signs/Symptoms of Local Irritation

At each study visit, beginning at Visit 1, Subjects will be evaluated for any signs and symptoms of local irritation [*Redacted*]. Baseline values will be used for comparative purposes against the scores documented at subsequent visits for each treatment group. Each Subject will be assigned a severity score by an Investigator based on the scale in Table 2.

Application site reactions [*Redacted*] will be recorded at each visit to allow a comparison between treatment groups.

## Table 3: Expected Application Site Reactions

[Redacted]

Subjects with a baseline irritation score of 3 (severe, marked/intense) will not be enrolled. After baseline, severe irritation (i.e., grade 3, described as severe or marked/intense) that requires treatment will be reported as an adverse event.

Local irritation reactions in the treatment area are common and the Investigator may instruct Subjects to stop the application of treatment ("rest period") to reduce Subject discomfort and to allow local skin reactions to subside based upon the Investigator's clinical assessment. Treatment should resume as soon as the reaction subsides sufficiently to allow reapplication. All dose modifications must be reported on the appropriate Study Medication Log & Dosing Compliance eCRF.

The treatment period should not be extended beyond 12 weeks due to missed doses or rest periods. Subjects whose condition worsens or lesions do not respond to treatment should be re-evaluated by the Investigator and management reconsidered.

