## 5.6 Adverse Events

An adverse event is defined as any untoward medical occurrence (sign, symptom or laboratory finding), regardless of severity and whether or not attributed to the investigational product. All adverse events, whether observed by an Investigator or Study Coordinator or reported by the Subject, whether related to study drug or not related to study drug, shall be documented on the eCRF and Subject records, together with details, i.e. date of onset, the duration and intensity of each episode, the action taken, the relationship to the investigational product and the degree of severity, the seriousness and the outcome.

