## 9.9 Safety Assessment

The extent of exposure will be summarized using descriptive statistics. No inferential analyses are planned.

Incidence of all adverse events reported during the study will be summarized using the MedDRA dictionary by treatment group, body system, severity, and relationship to study drug. The comparability of the Test and Placebo treatment groups for the frequency and severity of any adverse event that occurs in at least 5% of the Subjects in either treatment group will be evaluated using categorical methods.

Incidence of concomitant medications will be summarized by treatment group.

Safety analyses will be performed on the safety population. All safety data will be listed by treatment and Subject in data listings.

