## 10. ADVERSE EVENTS

## **10.1** Reporting of Adverse Events

Any untoward medical occurrence in a Subject or clinical-trial Subject administered a medicinal product and which does not necessarily have to have a causal relationship with this treatment. An adverse event can therefore be any unfavorable and unintended sign, symptom, or disease temporally associated with the use of a medicinal product, whether or not considered related to the medicinal product.

Any adverse event associated with the use of a drug in humans, whether or not considered productrelated, including the following: An adverse event occurring in the course of the use of a drug product in professional practice; an adverse event occurring from drug overdose whether accidental or intentional; an adverse event occurring from drug abuse; an adverse event occurring from drug withdrawal; and any failure of expected pharmacological action. Reporting an adverse event does not necessarily reflect a conclusion that the product caused or contributed to the adverse event.

All adverse events, whether observed by an Investigator or Study Coordinator or reported by the Subject, whether related to study drug or not related to study drug, shall be documented in the CRF and Subject records, together with details of the duration and intensity of each episode, the action taken, the relationship to the Investigational Product and the degree of severity, the seriousness and the outcome.

[*Redacted*]The Principal Investigator must strive to follow the Subject until the adverse event has resolved, becomes clinically insignificant, is stabilized or the Subject is lost to follow-up. The Principal Investigator must immediately report to the Contract Research Organization, by telephone and follow-up in writing, all study drug discontinuations due to adverse events.

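### Section 5.5 sets a narrower rule for reporting local irritation as an adverse event than Sections 5.6 and 10.1, so a reaction that interrupts dosing without being medicated can stay out of the AE tables

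*Combined protocol and SAP*

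**What the plan says.** Section 5.5 (text under Table 3) sets two conditions, grade and need for treatment: after baseline, "severe irritation (i.e., grade 3, described as severe or marked/intense) that requires treatment will be reported as an adverse event". The next paragraph calls local reactions common and says that "the Investigator may instruct Subjects to stop the application of treatment" until the reaction subsides. The interruption has its own destination: "All dose modifications must be reported on the appropriate Study Medication Log & Dosing Compliance eCRF". That paragraph does not mention AE recording.

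The general rules carry neither condition. Section 5.6: "An adverse event is defined as any untoward medical occurrence (sign, symptom or laboratory finding), regardless of severity". Section 10.1: "An adverse event can therefore be any unfavorable and unintended sign, symptom, or disease temporally associated with the use of a medicinal product". Both sections require all AEs to be documented with the action taken, and the severity scale after Section 10.1 includes mild and moderate events.

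Section 9.9 tabulates the AEs that were reported and compares the arms, by categorical methods, on "any adverse event that occurs in at least 5% of the Subjects in either treatment group". It summarises extent of exposure descriptively. Section 9.11 plans a separate descriptive comparison of application site reactions by arm, and of face against body.

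**The concern.** Two rules cover the same event. Under Sections 5.6 and 10.1, irritation that makes the Investigator stop application is an untoward sign with an action taken, and so an AE. Under Section 5.5, the same irritation must be reported as an AE when it is grade 3 and requires treatment. Stopping application is not described as treatment, and the visible text does not define when a reaction requires treatment. A grade 3 reaction that is rested and settles therefore lies outside the Section 5.5 sentence, while the same reaction given a medication lies inside it.

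Safety is part of the objective (Section 2), and Section 5.5 expects these reactions to be common. If sites apply Section 5.5 as a threshold, the AE incidence of irritation partly measures site habit. With approximately 5 sites (Section 4.1), one site's habit could move the overall rate. The outputs affected are the AE incidence table, its breakdown by severity and relationship, and the comparison triggered at 5%.

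**Working it through.** **Step 1. The two rules side by side.** For a reaction that is new or worse after baseline:

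| Reaction | Section 5.5 sentence, read as a threshold | Sections 5.6 and 10.1 |
|---|---|---|
| Grade 3, medicated | AE | AE |
| Grade 3, application stopped, not medicated | not covered | AE |
| Below grade 3, application stopped | not covered | AE |
| Below grade 3, application continued | not covered | AE |

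The rules agree only in the first row. The second and third rows are the reactions that interrupt dosing.

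**Step 2. Where each record is analysed.**
- An AE entry goes to the Section 9.9 incidence tables and can trigger the 5% comparison.
- A visit irritation score goes to the Section 9.11 descriptive comparison.
- A rest period goes to the dosing log. Section 9.9 summarises extent of exposure and lists all safety data. No visible text tabulates rest periods by arm or links them to the irritation scores.

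**Step 3. Can the rule matter for the 5% comparison?** The plan gives no irritation rates, so there is no figure of its own to reproduce. The rates below are assumptions, shown as a range.

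Inputs: about 300 subjects randomised 1:1 (Synopsis; Section 3) gives n = 150 per arm. The trigger is 0.05 × 150 = 7.5, so 8 subjects. It is also 8 at the 143 per arm of Section 9.2 (0.05 × 143 = 7.15).

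Let r be the share of an arm with irritation leading to a rest period, and s the share of those subjects whose reaction is also grade 3 and treated. The expected AE count is 150r if all are reported, and 150rs if only those meeting the Section 5.5 condition are reported. The chance of reaching the trigger is P(X ≥ 8), with X binomial (150, r) or (150, rs).

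| r | All reported: expected; P(X ≥ 8) | s = 5% | s = 10% | s = 25% | s = 50% |
|---|---|---|---|---|---|
| 5% | 7.5; 0.477 | 0.38; <0.001 | 0.75; <0.001 | 1.88; 0.001 | 3.75; 0.036 |
| 10% | 15; 0.986 | 0.75; <0.001 | 1.5; <0.001 | 3.75; 0.036 | 7.5; 0.477 |
| 20% | 30; 1.00 | 1.5; <0.001 | 3.0; 0.011 | 7.5; 0.477 | 15; 0.986 |
| 30% | 45; 1.00 | 2.25; 0.002 | 4.5; 0.083 | 11.25; 0.882 | 22.5; 1.00 |

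The choice of rule can decide whether irritation enters the comparison at all, but not everywhere in the range. At r = 20% with s = 50%, and at r = 30% with s = 50%, the trigger is reached under either rule with probability 0.986 or more. The table treats irritation as one AE term. If it is coded to several terms, each is less likely to reach 5% under both rules.

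**The case against.** **Section 5.5 does not say that other irritation is not an AE.** It can be read as a minimum: when a scored, expected reaction must also be entered as an AE, with Sections 5.6 and 10.1 still covering the rest. This stands as a reading. But a sentence that adds a grade and a treatment condition does little unless it limits reporting, and on the minimum reading sites still hold two rules for one event.

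**The reactions are captured elsewhere.** This stands, and it limits the point. A reader might infer that dose-limiting reactions go unseen between visits two weeks apart. The documents do not support that:
- Section 4.5 calls for assessment as soon as possible, at an Unscheduled Visit, when a reaction suggests sensitivity or irritation.
- Section 7.1 tells subjects to call the site about severe local skin reactions and to record AEs in the diary.
- Under Section 7.4, an Unscheduled Visit carries the interim-visit procedures, which include irritation scoring (Section 7.2).
- A rest period is itself given on the Investigator's assessment.

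The scores are compared by arm under Section 9.11. Section 10.1 requires immediate reporting of drug discontinuations due to AEs, and Section 9.13 summarises reasons for termination by arm. What these do not supply is a by-arm account of temporary interruptions.

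**Separating expected local reactions from AEs can be deliberate.** It can. In that case Sections 5.6 and 10.1 should state the exception, and at present their visible text does not.

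**Redaction.** The content of Table 3, the reaction scale and part of Section 10.1 are blacked out and may hold a linking rule. Confidence is limited accordingly.

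**Conclusion.** The visible text of Section 5.5 conflicts with Sections 5.6 and 10.1 on when local irritation is an AE. Read as a threshold, it lets a reaction that interrupts dosing without being medicated stay out of the AE tables and the 5% comparison. The conclusion rests on three assumptions: that sites treat the Section 5.5 sentence as a limit, that a rest period is not itself treatment, and that the redacted text holds no resolving rule.

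The size cannot be fixed from the documents. The range in the working shows that the rule can be decisive for the 5% trigger at some plausible rates and irrelevant at others. A reader might go further and infer that the active product will look better tolerated than it is. The documents do not support that: they give no irritation rate for either arm, and Section 9.11 compares the scored reactions by arm in any case. This is a gap in recording and tabulation that should be closed; it is not evidence of a biased safety profile.

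**What to change.** The changes concern recording and reporting only. When a rest period is given stays as it is.

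1. Reconcile Section 5.5 with Sections 5.6 and 10.1. State whether Section 5.5 is an intended exception for expected reactions scored and analysed under Section 9.11. If it is, say so in Sections 5.6 and 10.1 as well, because reactions below grade 3 that lead to no action would otherwise still be AEs on the wording of those sections.
2. Within that rule, record as an AE, with the action taken, any post-baseline local reaction that leads to a rest period, other dose modification, discontinuation or treatment, and any grade 3 reaction. AE status then no longer depends on whether a site rests or medicates.
3. In Sections 9.9 and 9.11 add, by arm, the number and percentage of subjects with at least one rest period and the number of rest days, from the dosing log already collected. Flag irritation scores taken during a rest period.

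The cost is one reconciled protocol sentence with its cross-references, and by-arm summaries from data already on the eCRF. The downside is more AE entries and possibly a higher reported AE rate.
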